4.3 Duration of Study Participation

Each subject will be followed at study specific visits until he/she has completed 24 months of follow-up after implantation (irrespective of patency status). After 24 months, subjects with a patent study conduit will be followed (while the study conduit remains patent) for up to 5 years (60 months) post-implantation at routine study visits.

The expected duration of the clinical investigation is 76 months (initiation of enrollment through completion of data collection).

5. STUDY POPULATION

5.1 Description of the Study Population

The study population will consist of subjects with ESRD who require hemodialysis and are targeted for implantation of an AV graft for dialysis access.

5.1.1 Inclusion Criteria

1. Subjects with ESRD who are not, or who are no longer candidates for creation of an autologous AV fistula and therefore need placement of an AV graft in the arm (upper- or forearm) to start or maintain hemodialysis therapy.
2. Either on hemodialysis or expected to start hemodialysis within 12 weeks of study conduit implantation.
3. At least 18 years of age at Screening.
4. Suitable anatomy for implantation of straight or looped conduits in either the forearm or upper arm (not crossing the elbow).
5. Hemoglobin ≥ 8 g/dL and platelet count $\geq 100,000$ cells/mm³ prior to Day 0 (within 35 days).
6. Other hematological and biochemical parameters within a range consistent with ESRD prior to Day 0 (within 35 days).
7. Adequate liver function prior to Day 0 (within 35 days), defined as both of the following:
 - a. ≤ 2 times upper limit of normal (ULN) for serum bilirubin, aspartate transaminase (AST), and alanine transaminase (ALT)
 - b. ≤ 1.5 for International Normalized Ratio (INR) or prothrombin time (PT) ≤ 18 seconds unless the subject is taking an anticoagulant at the time
8. Female subjects must be either:
 - a. Of non-childbearing potential, which is defined as post-menopausal (at least 1 year without menses prior to Screening) or documented surgically sterile or post hysterectomy (at least 1 month prior to Screening)
 - b. Or, of childbearing potential, in which case:
 - i. Must have a negative serum or urine pregnancy test at Screening, and
 - ii. Must agree to use at least one form of the following birth control methods for the duration of the study:
 1. Established use of oral, injectable or implanted hormonal methods of contraception

2. Placement of an intrauterine device or intrauterine system
3. Barrier methods of contraception: condom or occlusive cap (diaphragm or cervical/vault caps) with spermicidal foam/gel/film/cream/suppository
9. Subject, or legal representative, able to communicate effectively with investigative staff, competent and willing to give written informed consent, and able to comply with entire study procedures including all scheduled follow-up visits.
10. Life expectancy of at least 1 year.

5.1.2 Exclusion Criteria

1. History or evidence of severe peripheral vascular disease in the intended arm for implantation.
2. Known or suspected central vein stenosis or conduit occlusion on the ipsilateral side of the planned implantation, unless the stenosis is corrected prior to study conduit implantation.
3. Treatment with any investigational drug or device within 60 days prior to study entry (Day 0) or ongoing participation in a clinical trial of an investigational product.
4. Cancer that is actively being treated with a cytotoxic agent.
5. Documented hyper-coagulable state.
6. Bleeding diathesis.
7. Active clinically significant immune-mediated disease, not controlled by maintenance immunosuppression.
 - a. Low dose glucocorticoid therapy (e.g. up to 10mg a day prednisone or prednisolone) is acceptable.
 - b. High dose glucocorticoid therapy for treatment of autoimmune flare, or other inflammatory diseases is excluded.
 - c. Patients using glucocorticoids for immunosuppression post-transplant to prevent against transplanted allograft rejection in the period post allograft failure are excluded.
 - d. The following examples of immunosuppressive agents (or the like) are exclusionary for enrollment in this clinical trial:
 - i. tacrolimus or FK506 [Prograf]
 - ii. mycophenolate mofetil [Cellcept],
 - iii. cyclosporine [Sandimmune or Gengraf]
 - iv. Sirolimus administered systemically (Sirolimus in drug eluting stents is NOT an exclusion)
8. Anticipated renal transplant within 6 months.

9. Venous outflow from study conduit cannot be placed more centrally than the venous outflow of any previous failed access on that extremity.
10. Active local or systemic infection (white blood cells [WBC] > 15,000 cells/mm³ at Screening). If the infection resolves, the subject must be at least one week post resolution of that infection before implantation.
11. Known serious allergy to planned antiplatelet agent.
12. Pregnant women, or women intending to become pregnant during the course of the trial.
13. Any other condition which in the judgment of the investigator would preclude adequate evaluation of the safety and efficacy of the study conduit.
14. Previous enrollment in this study or any other study with HAV.
15. Employees of Humacyte and employees or relatives of the investigator.

5.2 Randomization

After a subject completes the Screening assessments, the Principal Investigator will review the subject's inclusion/exclusion criteria to determine the subject's eligibility. The Screening pages of the electronic case report form (eCRF) for eligible subjects will then be reviewed and eligibility confirmed by the Medical Monitor prior to randomization.

Study site personnel will randomize the subject to either HAV or ePTFE during surgery (i.e., after the surgical site [upper- vs fore-arm] has been selected and after confirmation that the subject is not a candidate for creation of an autologous AV fistula). Randomization may only occur once the arterial and venous exposures have been completed with confirmation of adequate arterial inflow and venous outflow. The randomization schema will ensure that subjects will be assigned on a 1:1 basis to the HAV or ePTFE arms of the study. The randomization will be stratified by the upper arm or forearm placement based on the Investigator's determination of where the study conduit should be located.

6. INVESTIGATIONAL MEDICINAL PRODUCT

Additional information on the manufacturing process and testing of HAV is provided in the Investigator Brochure.

6.1 Human Acellular Vessel

6.1.1 Product Description

The IMP is Humacyte's human acellular vessel (HAV), which is a tissue-engineered vascular conduit for hemodialysis access in patients with ESRD. It is a sterile, non-pyrogenic acellular tubular conduit composed of human collagen types I and III plus other ECM proteins, including fibronectin and vitronectin. The HAV is 6 mm in diameter and approximately 42 cm in length. The product is supplied on a silicone mandrel immersed in sterile, phosphate buffered saline in a sealed and labeled plastic container.

6.1.2 Manufacturer of the Investigational Medicinal Product

The HAV is manufactured by:

AlloSource
[name]
[name]

Traceability of the HAV during and after the clinical investigation will be achieved by the assignment of lot numbers. A unique identifying lot number will be assigned to each vessel.

6.1.3 Packaging, Storage, and Labeling

Packaging: Each HAV is contained in a sealed, flexible plastic primary container closure system that was developed by Humacyte. The system meets container/closure requirements to maintain sterility as well as product and fluid integrity. The vessel is contained inside the system in a fixed manner, immersed in a sterile, phosphate buffered saline. The total volume of the storage solution is approximately 300 mL.

Storage: The product is shipped under controlled conditions to maintain temperature at 4°C (range: 2 – 10°C). The product should be stored in a refrigerator that maintains this temperature range. The HAV MUST NOT be allowed to freeze.

Labeling: The IMP will be labeled according to applicable guidelines and relevant regulatory agency requirements. A tamper resistant label affixed to the secondary container will be used to ensure that the product is not compromised prior to use.

6.1.4 Implantation of the Humacyte Human Acellular Vessel

The Humacyte HAV is implanted using standard vascular surgical techniques similar to placement of synthetic or biologic AV grafts (see study manual for details).

The HAV must be delivered through the subcutaneous tissue by means of a sheath tunneler. During tunneling, the HAV should be passed through the tunneler sheath with the silicone mandrel in place to facilitate ease of delivery (see study manual for details).

6.2 Comparator Grafts

6.2.1 Product Description

The comparator in this study is one of the following commercially available 6 mm ePTFE grafts:

- Gore® PROPATEN® Vascular Graft (6mm x 40cm, straight, standard wall, non-stretch, non-tapered)
- Bard® Impra® Vascular Graft (6mm x 40cm, straight, standard wall, non-stretch, non-tapered)

6.2.2 Manufacturer of Comparator Grafts

The comparator grafts are manufactured by:

- W.L. Gore & Associates, Inc.
Flagstaff, AZ 86004 USA
- Bard Peripheral Vascular, Inc.
Tempe, AZ 85281 USA

Traceability of the comparator grafts during and after the clinical investigation will be achieved by tracking lot numbers for each graft.

6.2.3 Storage

The storage of the comparator grafts should follow the approved Product Information for the respective products.

6.2.4 Implantation of the Comparator Grafts

Implantation of the comparator grafts will follow standard vascular surgical techniques described in the approved Instructions for Use for the respective products.

6.3 Investigational Medicinal Product Accountability Procedures

6.3.1 Human Acellular Vessel

HAVs will be provided by Humacyte. Documentation of receipt, dispensing, and return of the HAVs must be maintained by the Principal Investigator or his/her designee. It is the Principal Investigator's responsibility to ensure that the HAVs are kept in a secure location, with access limited to individuals authorized by the Principal Investigator. The HAVs will be shipped by Humacyte or a designated representative with the IMP Receipt Form. Once signed, the IMP Form should be returned to Humacyte, and the original will be maintained in the Investigator's Files. The HAV Accountability Log will be used to account for all HAVs received, dispensed, and returned and must be maintained by the site until the conclusion of the study, at which time the original will be retrieved by Humacyte or its authorized designee and a copy kept at the site. Following final accountability of the HAVs by Humacyte or its authorized designee, all unused HAVs will be returned to Humacyte or destroyed according to procedures agreed upon with Humacyte.

6.3.2 Comparator Grafts

The comparator grafts will be provided by the study sites through commercially available stock, or by Humacyte via a third party distributor. The lot numbers for each graft used during the study will be documented.

7. OTHER TREATMENTS AND MEDICATIONS

7.1 Prior and Concomitant Medications

Prior medications are defined as all prescription medications plus aspirin taken within 7 days (whether continuing or not) prior to surgery (Day 0). All prior and concomitant medications (including immediately pre-surgery and post-surgery medications) must be listed in the subject's medical record and recorded in the eCRF (as defined in [Section 8](#)).

Drugs used during anesthesia should be recorded in the anesthesia records but should not be transcribed in the eCRF.

Subjects should be questioned at each study visit concerning any new medications or changes in current medications (does not include IV fluids).

For antibiotics, the following information will be recorded in the eCRF:

- Medication generic name / components of combination product
- Dose
- Route of administration
- Frequency of administration
- Date started
- Date stopped
- Indication for use

For all other medications taken during the study, only medication name, indication for use and start and stop dates will be recorded in the eCRF.

7.2 Essential and Restricted Medications

7.2.1 Essential Medications

All subjects should receive both antibiotic and antithrombotic therapy in conjunction with HAV and ePTFE graft implantation:

Antibiotic prophylaxis:

All subjects must have at least 1 dose of antibiotic prophylaxis in accordance with local institutional guidelines. Longer antibiotic prophylaxis is at the discretion of the Principal Investigator.

Antithrombotic prophylaxis:

Intra-operative heparin: Use, dose, and route of administration of heparin during surgery are at the discretion of the investigator.

Each subject will be required to take daily aspirin (75 to 325 mg) unless he/she is already taking another antiplatelet agent. Aspirin should be initiated no later than the day after surgical implantation of the study conduit (Day 1). If low molecular weight heparin (LMWH) is administered post-operatively, aspirin or other antiplatelet agent should be initiated after stopping LMWH.

Aspirin is the recommended agent to be used for antiplatelet therapy and generally should not be combined with a second antiplatelet agent unless there is a specific indication for dual antiplatelet therapy (such as a drug eluting stent). Subjects who are known to be aspirin-sensitive should take another antiplatelet agent at the discretion of the investigator.

Anticoagulation is contraindicated unless there is a specific indication, such as deep vein thrombosis, pulmonary embolism, or atrial fibrillation. Patients already on anticoagulation at the time of screening for an appropriate medical indication can be enrolled in to the study, provided their screening data (INR, PT) at the time of medical director review indicates that it is being appropriately managed. Such patients do not require antiplatelet therapy with aspirin. Anticoagulation should be interrupted during a short perioperative window (as determined by standard of care for the site depending upon the indication for anticoagulation) and then resumed as soon as it is appropriate. If anticoagulation therapy ceases during the study the patient should start antiplatelet therapy (preferably with aspirin) as soon as possible.

7.2.2 Restricted Medications

Direct thrombin inhibitors, Factor Xa inhibitors, and vitamin K antagonists should only be given if there is a specific indication for their use.

8. STUDY PROCEDURES / EVALUATIONS

8.1 Screening (Baseline) (Day -35 to Day 0)

The screening period time window is currently specified as a maximum of 35 days from the day of consent until the day of surgery. In certain cases, the originally scheduled day of study surgery may need to be delayed due to purely logistical reasons and the subject's screening assessments may no longer fall within the current protocol-specified screening period time window. If there has been no significant change in the medical condition of the subject, it should not be necessary to repeat screening assessments or to reconsent the subject prior to study surgery. However, any extension of the screening period time window specified in the protocol, even though only for logistical reasons, must be discussed with and approved by the medical monitor prior to the day of study surgery. Subjects who have had significant medical events since screening and are now outside of the original screening window will need to be rescreened. Any relevant clinical data collected as part of standard of care since the initial screening that is within the allowed window for surgery may be used for rescreening purposes.

8.1.1 Informed Consent

The subject's informed consent must be obtained prior to any study-related procedures/activities, using the site's Institutional Review Board (IRB) / Independent Ethics Committee (IEC) approved consent form. The informed consent will cover:

- Agreement to participate in the trial for the full 5 years;
- Willingness to have study-specific medical information collected if the subject desires to stop coming for study visits. It should be noted that consent for this information collection is not a requirement for participation in the study;
- Willingness to have discarded parts of the implanted study conduit collected for histology. It should be noted that consent for collection of histology is not a requirement for participation in the study.

8.1.2 Demographics

The subject's age, gender, race and ethnicity will be recorded.

8.1.3 Medical History

A detailed medical history for each subject, including cause(s) of renal failure, history of dialysis and past vascular access procedures and smoking history will be obtained during Screening. All relevant past and present conditions that have occurred in the last 5 years will be recorded, as well as prior surgical procedures (including renal transplant history, if applicable).

8.1.4 Prior and Concomitant Medications

Record all prescription medications and aspirin that the subject is taking or has taken within 7 days prior to surgery in the subject's medical record and eCRF (see Section 7.1).

8.1.5 Physical Exam, Vital Signs and Temperature

A complete physical exam (PE) will be performed during Screening (including height and weight). The investigator or qualified medical personnel who routinely perform these evaluations in this patient population will conduct the examination, determine findings, and assess any abnormalities with respect to clinical significance. The subject's sitting blood pressure, resting heart rate and temperature will also be obtained. The patient should be carefully examined for signs or symptoms of central vein pathology as well as assessment of adequate arterial inflow.

Standard of care physical exams conducted prior to consent may be used for determination of eligibility provided they are within the screening period time window and all required data are available.

8.1.6 Electrocardiogram

A 12-lead electrocardiogram (ECG) will be performed during Screening. A standard of care 12-lead ECG completed prior to consent may be used for determination of eligibility provided it occurred within the screening period time window.

8.1.7 Laboratory Evaluations

During Screening blood will be collected for the following:

- Hematology: hemoglobin, hematocrit, red blood cell (RBC), WBC with differential, platelet count.
- Clinical chemistry: sodium, potassium, calcium, blood urea nitrogen (BUN) or urea, creatinine, albumin, total bilirubin, ALT, AST, alkaline phosphatase, glucose (non-fasting).
- INR or PT (if INR value is not available)
- PRA

Additionally, either a urine sample will be obtained for women of childbearing potential to perform a urine pregnancy dipstick test or a serum pregnancy test will be performed.

Standard of care laboratory evaluations conducted prior to consent may be used for determination of eligibility provided they are within the screening period time window.

8.1.8 Vessel Mapping

Vessel mapping will be performed during Screening to determine whether the vessels in the operative limb are suitable for conduit implantation. Vessel mapping performed by ultrasound in the clinic by the investigator is acceptable. If adequate vessel mapping has been undertaken within the 8 weeks prior to the start of Screening and there has been no significant change in the condition of the subject (including insertion of CVC) then repeat vessel mapping is at the discretion of the Principal Investigator.

8.1.9 Document Reason for Not Creating a Fistula

The Principal Investigator will document the reasons why an AV graft will be implanted rather than an AV fistula created.

8.1.10 Assessment of Central Vein Stenosis

The absence of central vein stenosis will be determined by clinical criteria. If central vein stenosis or occlusion on the side in which implantation of the study conduit is planned is identified / suspected, it must be corrected before randomization.

8.1.11 Review of Eligibility for Randomization

After review by the Principal Investigator, the subject's Screening eCRFs will be provided to the Medical Monitor for review and confirmation of eligibility prior to randomization.

8.1.12 Serious Adverse Events

Only serious adverse events (SAEs) associated with screening procedures will be collected during the Screening period beginning from the time the subject signs the informed consent form. See [Section 9](#) for information regarding AE/SAE collection and data handling.

8.2 Randomization and Surgical Placement of the HAV or the ePTFE Graft (Day 0)

8.2.1 Medical History and Concomitant Medications

The subject's medical history and concomitant medications (prescription medications and aspirin use) will be updated (if changed) prior to surgery. Drugs used during anesthesia should be recorded in the anesthesia records but should not be transcribed in the eCRF.

8.2.2 Symptom-directed Physical Examination, including Temperature

Perform a symptom-directed PE (if needed) and document in eCRF subject's temperature (at all visits irrespective of symptoms). The investigator or qualified medical personnel who routinely

perform these evaluations in this patient population will conduct the examination, determine findings, and assess any abnormalities with respect to clinical significance.

8.2.3 Confirmation of Eligibility and Randomization

After a subject completes the Screening assessments, the Principal Investigator will review the subject's inclusion/exclusion criteria to determine the subject's eligibility. The Screening pages of the eCRF for eligible subjects will then be reviewed and eligibility confirmed by the Medical Monitor prior to randomization.

Study site personnel will randomize the subject to either HAV or ePTFE during surgery (i.e., after the surgical site [upper- vs fore-arm] has been selected and after confirmation that the subject is not a candidate for creation of an autologous AV fistula). Randomization may occur once the arterial and venous exposures have been completed with confirmation of adequate arterial inflow and venous outflow. The randomization schema will ensure that subjects will be equally assigned on a 1:1 basis to the HAV or ePTFE arms of the study. The randomization will be stratified by upper arm or forearm placement based on the Principal Investigator's determination of where the study conduit should be located.

8.2.4 Surgical Placement

Document the surgical procedure for implantation, including the location of the study conduit, and any complications immediately postoperatively. Indicate whether subject remained in the hospital the night after surgery; if so, indicate whether the overnight stay was planned and whether it was related to the surgery or some other reason.

8.2.5 Confirmation of Patency

Patency of, and adequate flow in, the study conduit will be confirmed intraoperatively or immediately post-surgery by the investigator's preferred method (eg. Physical exam, Doppler, ultrasound, etc) (to be documented).

8.2.6 Adverse Events

All adverse events (AEs) will be collected beginning on Day 0 after implantation up to 2 years post-implantation (Month 24). The subject will be asked general questions about his/her health and for any conduit or dialysis problems since the previous visit. See [Section 9](#) for information regarding AE collection and data handling.

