9.4 Reporting of Adverse Events

At each evaluation, the subject will be questioned in a general way and no specific symptoms will be suggested. If any AEs have occurred, they will be recorded on the AE pages of the eCRF and in the subject's medical record. If known, the diagnosis should be recorded in preference to the listing of individual signs and symptoms.

During the Screening period (Day -35 to Day 0 prior to implantation), only SAEs related to study procedures will be reported beginning at the time the subject signs the informed consent form. From Day 0 after implantation to 2 years post-implantation (Month 24 visit) or ET visit, whichever occurs earlier, all AEs will be reported.

During the long-term follow-up period from 2 years to 5 years post-implantation, only the following will be reported by the investigator:

- All SAEs considered related to the HAV
- All Events of Special Interest.

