9: Dialysis efficiency (spKt/Vurea) and additional lab data (hemoglobin, ESA used and dose and HbA1c) will be obtained from dialysis organizations for a subset of subjects via data transfers to the CRO. These data will be obtained from labs drawn at the discretion of the dialysis unit; where feasible and appropriate, these data will be obtained prior to study conduit implantation, too (HbA1c will be obtained pre-implantation only, when possible). No site involvement is required in this process.

10: Only SAEs related to the screening procedures will be reported during the Screening period. All AEs will be reported from Day 0 after implantation up to the Month 24 visit. After the Month 24 visit up to Month 60, only the following will be reported by the investigator:

- All SAEs considered related to the HAV
- All Events of Special Interest.

11: Subjects will be assessed at a study visit that can occur anytime from Day 7 to 15.

12: Subjects withdrawn prior to the Month 60 visit will have ET assessments performed. Subjects withdrawn prior to Month 24 should complete an ET visit that correlates with the procedures at Month 24. Subjects withdrawn after Month 24 and prior to Month 60 should complete an ET visit that correlates with procedures post Month 24 through Month 60.

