## 4.2 ANALYSIS SETS

The primary analysis will be based on the Intent-to-Treat (ITT) analysis set defined as all randomized subjects (based on study conduit group assignment).

The following rules will apply to the ITT analysis set:

- Subjects in whom the wrong conduit is implanted (e.g. an HAV implanted in a subject randomized to an ePTFE graft) will be analyzed within their randomized group rather than in their implanted group
- Subjects in whom no study conduit was implanted will be considered as if abandoned on Day 0 and included in their randomized group
- Subjects in whom the site (upper vs forearm) of implantation is different from the intended site will be analyzed based on the intended site.

The analysis will be repeated using the modified Intent-to-Treat (mITT) analysis set defined as all subjects in whom a study conduit has been implanted (based on actual conduit implanted and the actual site).

A secondary analysis will be conducted in a Per Protocol (PP) analysis set defined as all subjects in whom a study conduit has been implanted (based on actual conduit implanted) and in whom there were no major protocol deviations or data integrity concerns.

Major protocol deviations will be reviewed and verified at the time of determination, the time between the database soft lock and hard lock. Humacyte will identify major protocol deviation categories prior to the close of the database for the primary, second and final analysis. An overall major protocol deviation listing will be reviewed just prior to database lock for final analysis. Humacyte will approve all final major protocol deviation determinations. The protocol deviations SAS dataset will then be generated but will not be entered into the database.

Safety analysis will be conducted using the safety analysis set, which is defined as all subjects who receive study treatment, with the subject's treatment group based on the treatment that was received.

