## 7.2 ADVERSE EVENTS

See the study protocol for the definition of adverse events (AE). The investigator's verbatim term for all adverse events will be mapped to System Organ Class (SOC) and preferred terms using the current version of the Medical Dictionary for Regulatory Activities (MedDRA).

From a technical regulatory perspective the HAV is a biologic medicinal product while the ePTFE graft is a device. For the purposes of this study and to allow for better cross-treatment arm comparisons of safety, and given that the IMP is a biologic drug, all events will be reported as if both arms were drugs.

AEs will be summarized as treatment-emergent AEs (TEAEs) for the Safety analysis set.

An AE will be considered a TEAE if the onset of the event is on or after the start of the anesthesia for the implant surgery. If an AE start date is completely missing, then the AE will be considered as TEAE unless it can be determined that the AE end date occurred prior to the anesthesia for the implant surgery. If the AE start date is partially missing then the start date will be imputed as described in Section 4.4.

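### Full AE collection starts only after implantation, so non-serious AEs between randomisation and completed implantation fall outside the protocol's window although the SAP counts events from anaesthesia

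*Protocol*

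**What the plan says.** **Start of AE collection.** Protocol 8.2.6 says "All adverse events (AEs) will be collected beginning on Day 0 after implantation up to 2 years post-implantation (Month 24"). Protocol 9.4 says "From Day 0 after implantation to 2 years post-implantation (Month 24 visit) or ET visit, whichever occurs earlier, all AEs will be reported", and footnote 10 of Appendix 1 says "All AEs will be reported from Day 0 after implantation up to the Month 24 visit".

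**Before that point.** Protocol 9.4 defines the earlier period as "During the Screening period (Day -35 to Day 0 prior to implantation") and says that in it "only SAEs related to study procedures will be reported beginning at the time the subject signs the informed consent form".

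**Randomisation.** Protocol 5.2 places it during surgery: "Randomization may only occur once the arterial and venous exposures have been completed". Protocol 8.2.3 and 10.1 agree.

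**Treatment-emergent AEs.** SAP 7.2 counts an AE as treatment-emergent "if the onset of the event is on or after the start of the anesthesia for the implant surgery".

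**Safety set.** SAP 4.2 has it "defined as all subjects who receive study treatment, with the subject's treatment group based on the treatment that was received". Protocol 10.2 gives the same definition. In the ITT efficacy analysis, a randomised subject with no conduit implanted counts as an abandonment on Day 0 (Protocol 10.3.2, SAP 4.2).

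**The concern.** Once a subject is randomised, everything that happens belongs to the randomised comparison. Here the first thing that happens is placement of the allocated conduit, and the stated start of AE collection comes after it. The SAP's AE tables are defined over a period that includes placement, so a reader would take them as complete for it. On the protocol's wording they are not.

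Placement instructions are not identical in the two arms. Protocol 6.1.4 requires the HAV to go through a sheath tunneler with its mandrel in place, while 6.2.4 refers the ePTFE grafts to their own instructions for use. Protocol 2.4.3.2 links very early failures to surgical technique. Protocol 4.2.3 also directs iatrogenic injuries to the AE route and away from the Events of Special Interest. For a non-serious injury during placement, that route is not yet open. At stake is the completeness of the AE comparison for this short interval, most of all for a subject whose implantation is attempted and fails.

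**Working it through.** No arithmetic applies. The check sets the start points and reporting routes side by side.

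**1. Order of events on Day 0**

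| Step | Rule that opens | Source |
|---|---|---|
| Start of anaesthesia | Treatment-emergent window | SAP 7.2 |
| Artery and vein exposed, flow confirmed | none | Protocol 5.2 |
| Randomisation | Randomised comparison | Protocol 5.2, 8.2.3, 10.1 |
| Placement of the allocated conduit | none | Protocol 6.1.4, 6.2.4 |
| After implantation | Collection of all AEs | Protocol 8.2.6, 9.4, Appendix 1 fn 10 |

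The SAP window opens before the protocol's collection window. The part of the gap that matters for the treatment comparison runs from randomisation to completed implantation.

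**2. Is the boundary really inside the operation?** Protocol 9.4 divides Day 0 itself into a part before and a part after implantation, so the rule cannot be read as covering the whole day. Nothing defines implantation as the start of surgery.

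**3. What is captured in the gap by other routes**

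- Serious AEs: Protocol 9.4.1 requires every SAE in the study to be reported, related or not. Protocol 9.4 separately covers study-procedure SAEs before implantation.
- Surgical complications: Protocol 8.2.4 asks for those seen immediately after the operation. The Day 0 row of Appendix 1 has no such limit, and SAP 8 summarises and lists them. No severity or causality grading is specified for this record, and SAP 8 is separate from the AE tables of SAP 7.2.
- Non-serious AEs, as AEs: no route.

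**4. Scope of SAE reporting before implantation**

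| Section | SAEs covered |
|---|---|
| Protocol 8.1.12 | Linked to screening procedures |
| Protocol 9.4 | Linked to study procedures |
| Appendix 1 fn 10 | Linked to screening procedures |
| Protocol 9.4.1 | Any, related or not |

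An SAE caused by the operation before the conduit is in is reportable under 9.4 and 9.4.1, but not under the narrower wording of 8.1.12 and footnote 10.

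**5. Randomised but not implanted.** The efficacy rules foresee this subject. A collection window that opens after implantation never opens for this subject. The safety set requires receipt of study treatment, which on its plain reading is not met. The same subject can thus be an efficacy failure on Day 0 and absent from the safety analysis.

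**The case against.** The strongest reply is that little is lost. SAEs are reportable whatever the minute of onset, Day 0 complications are documented and summarised, and bleeding or injury still present once the conduit is in falls within the AE window. A treatment-emergent definition classifies the events that are reported and does not set what is collected. SAP 7.2 lists onset by date and day, with no clock time, so a reported Day 0 event would probably be counted anyway. Protocol 6.1.4 and 6.2.4 both speak of standard vascular technique, and 2.5.1 expects risks similar to those of marketed grafts.

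Most of this stands, and it rules out three stronger readings that a reader might infer:

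- *That harms during placement go uncollected, or that a failed implantation leaves no safety record.* The SAE and complications routes contradict both. The AE definition in Protocol 9.1 also reaches subjects who have only undergone study procedures.
- *That the safety set certainly excludes attempted but failed placements.* Exclusion is the likely reading, but the documents do not say whether an attempt counts as receiving treatment. The mITT and PP sets, by contrast, explicitly require an implanted conduit.
- *That the gap favours one arm.* The documents do not show that non-serious harm confined to placement differs by conduit.

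The reply does not close the narrower gap. Counting Day 0 events generously helps only if sites report them, and three passages tell sites to begin later. The complications record is not a substitute for graded, causally assessed AEs.

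**Conclusion.** The point holds for non-serious AEs. Those arising between randomisation and completed implantation are outside the protocol's collection window and, if sites follow the protocol, will be missing from the treatment-emergent tables that SAP 7.2 defines to include them. Two related defects hold as well: the inconsistent scope of SAE reporting before implantation, and the lack of a clear safety rule for subjects randomised but not implanted.

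All randomised subjects, planned as at least 350 (SAP 3.2.1), enter this interval. The documents give no intraoperative event rate and no expected number of failed implantations, so the number of AEs or subjects affected cannot be stated. The primary efficacy analysis is not touched. The conclusion rests on reading *after implantation* as after the conduit is in place, which the before/after split of Day 0 in Protocol 9.4 supports.

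**What to change.** - **Protocol 8.2.6, 9.4 and Appendix 1 footnote 10:** start collection of all AEs at the start of anaesthesia for the implant surgery, to match SAP 7.2, and flag each Day 0 onset as before or after randomisation. This start also applies to subjects in whom no conduit is implanted.
- **Protocol 8.1.12, 9.4 and footnote 10:** give one scope for SAE reporting before implantation, consistent with 9.4.1.
- **Protocol 10.2 and SAP 4.2:** state that the safety set includes every randomised subject in whom placement of a study conduit was attempted, grouped by the conduit attempted.
- **Subjects already operated on:** take these events from the operative notes and the Day 0 complication records, or state the limitation in the SAP and the study report. Enrolment was planned to start in 2Q2016 and last 16 months, and this protocol version is dated August 2018. On those timings, this would apply to most or all subjects.

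Cost: rewording in a few places, a few more AE entries (some from before randomisation and unrelated to the conduit, which the flag separates), and some retrospective abstraction. Severity and causality assigned afterwards from records will be less reliable than prospective grading, so AEs recovered in this way should be identified as such.
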